### 6.5.2 *Serious adverse events (SAEs)*

Incidence of serious adverse event will be tabulated. Serious adverse events incidents will be summarized descriptively by part, center, system organ class/ preferred term, and treatment group.

### **6.5.3 *Laboratory data***

Descriptive statistics of original data and net changes in hematology and biochemistry data will be presented by part, center, visit, and treatment.

Results of clinical significance with regard to laboratory data will be summarized with frequency and percentage.

### **6.5.4 *Physical Examination (PE)***

Incidence table including umber and percentage of patient with abnormal PE will be tabulated by part, center, visit, and treatment for each body system.

The corresponding body system will be analyzed and reported using a transition table. The type of transition includes no change, change to normal, change to non-clinical significance, (NCS), change to clinical significance (CS) for each body system from baseline (Visit 2).

### **6.5.5 *Vital Signs***

Descriptive statistics of net changes in vital signs including systolic and diastolic blood pressure, heart rate and body temperature will be presented by part, center, visit, and treatment.

Results of clinical significance with regard to vital sign will be summarized with frequency and percentage.

### **6.5.6 *ECG***

Frequency table and change in ECG result will be summarized by part, center, visit and treatment. The transition of ECG is define as following 4 groups: no change, change to normal, change to non-clinical significance, (NCS), change to clinical significance (CS).

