1.2.2 Safety Pharmacology

In order to verify the possible effects other than antidepressant, five studies were conducted to evaluate the effects of PDC-1421 on central nervous system, autonomic system, cardiovascular function, respiratory function, gastrointestinal system, renal function, allergy, inflammation, metabolism and hERG tail current assay:

- EfficacyProfiling *in vivo*[®]

- Safety Pharmacology Testing Package
- AdverseEventProfiling *in vivo*®
- Safety Pharmacology test in Central Nervous System, Cardiovascular System and Respiratory System
- hERG tail current assay

The significant findings were summarized in Table 6.

Table 6. Summary of the finding in safety pharmacology

Study package	Study condition and findings
EfficacyProfiling	
 • Oral administration of PDC-1421 at 3000 mg/kg did not cause any significant change in vivo studies. • PDC-1421 at 300 µg/ml did not demonstrate any significant activity ($\geq 50\%$ change) in vitro studies.
Safety Pharmacology Testing Package	
PDC-1421 concentration at 300 µg/mL:
 
 • Decrease in acetylcholine and BaCl₂-induced constriction in guinea pig ileum.
AdverseEventProfiling in vivo ®	
PDC-1421 oral dose at 3000 mg/kg:
 
 • Inhibition of gastric emptying in fasted rats (-45%) 
PDC-1421 oral dose at 3000 mg/kg for 7 days:
 
 • Increase in RBC on day 2 in blood chemistry • Increase in K⁺ and decrease in glucose on day 2 in blood chemistry • Decrease in LDH (lactate dehydrogenase) on day 8 in blood chemistry
Safety Pharmacology test in Cardiovascular System	
 • RR interval elongation, heart rate decrease, diastolic arterial pressure decrease and increased sinoatrial arrest incidence were found in dogs in 2500mg/kg group. • Diastolic arterial pressure decrease was found in dogs in 2500mg/kg group.
hERG tail current assay	Below the dosage, 0.8mg/ml PDC-1421, should be viewed as the “no effect concentration” in this assay.

Few effects, including gastrointestinal effects, electrolytes equilibrium, blood sugar value, heart rate decrease and diastolic arterial pressure decrease were found in safety pharmacology. These findings provided scientific evidence in further clinical study to evaluate the influence of PDC-1421.

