1.4 Potential Risk and Benefit

1.4.1 Potential Risk

The toxicological profile of PDC-1421 was characterized in single and repeat oral dose studies of up to 13 weeks in rats and repeat oral dose studies of up to 28 days in dogs. Genetic toxicology and safety pharmacology have also been conducted. PDC-1421 was observed to be associated with some adverse effects in serum electrolytes and GI function, but none were clinically significant. Therefore, potential risks of PDC-1421 are fluctuated electrolyte level and gastrointestinal discomfort. We monitored these in the Phase I study and there was no deviation of electrolyte level and no significant gastrointestinal discomfort during monitoring in the clinical trial. However, there were non-clinically significant mild lower diastolic blood pressure and lower heart rate in dog telemetry study and it has been only with the 2500 mg/kg, which is around the NOAEL for dogs. The cardiovascular systems will be monitored in the clinical study.

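### The four change groups for ECG and physical examination put one kind of worsening and one kind of improvement under the same label; a 3x3 shift table would separate them at no data cost

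*SAP*

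**What the plan says.** **ECG (SAP 6.5.6).** Two outputs are planned. The first is general: "Frequency table and change in ECG result will be summarized by part, center, visit and treatment". The second is the four-group classification: "no change, change to normal, change to non-clinical significance, (NCS), change to clinical significance (CS"). The section does not say which visit is the baseline, and it names no ECG interval or rhythm variable.

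**Physical examination (SAP 6.5.4).** The classification is the same, measured from Visit 2: "The type of transition includes no change, change to normal, change to non-clinical significance, (NCS), change to clinical significance (CS) for each body system". The companion output is "Incidence table including umber and percentage of patient with abnormal PE will be tabulated", by visit and treatment for each body system. No split of abnormal findings into NCS and CS is stated for that table.

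**Related text.**
- Protocol 7.2 sets the pre-dose Visit 2 data as the safety baseline. SAP 6.5.7 uses Visit 1 for the C-SSRS and plans a shift table there.
- Exclusion criterion 6 (Protocol 4.2) removes patients with a clinically significant ECG, vital sign or laboratory value, if the investigator thinks it might interfere with the study.
- Protocol 1.2.2, Table 6, reports for the dog study: "RR interval elongation, heart rate decrease, diastolic arterial pressure decrease and increased sinoatrial arrest incidence were found in dogs in 2500mg/kg group". Protocol 1.4.1 adds: "The cardiovascular systems will be monitored in the clinical study".

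**The concern.** A change table in a safety report should show how many patients in each arm got worse and how many got better. Three of the four groups are named by the state reached, without the state left. For *change to normal* and *change to CS* that is enough to fix the direction. For *change to NCS* it is not, because NCS is the middle state and can be reached from either side. *No change* has a different weakness: it does not separate a patient who stayed normal from one whose clinically significant finding persisted.

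What is at stake is how readable two safety tables are in a trial with 60/3 = 20 patients per arm in Part II. At that size, a few patients under a mixed label can change the impression that a table gives.

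**Working it through.** The plan gives no figure to reproduce, so the check is an enumeration.

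**1. Map the transitions.** The three states are implied by the SAP's own labels: 3 x 3 = 9 cells.

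| Visit 2 state | later: normal | later: NCS | later: CS |
|---|---|---|---|
| normal | no change | to NCS (worse) | to CS (worse) |
| NCS | to normal (better) | no change | to CS (worse) |
| CS | to normal (better) | to NCS (better) | no change |

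*Change to NCS* is the only label with both directions: 2 of 9 cells. *No change* holds 3 cells, which differ in severity but not in direction.

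**2. Four counts alone.** They fix 4 of 9 unknowns. Take a hypothetical arm of 20 with 14 normal throughout, 2 moving from NCS to normal, and 4 in *change to NCS*. If those 4 came from normal, 4 worsened and 2 improved. If they came from CS, 0 worsened and 6 improved. The four-group table is the same.

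**3. Add the ECG frequency table.** Assume that it has three levels, includes Visit 2 and covers the same patients.
- Each *no change* cell follows by subtraction; for example, CS to CS = (CS at visit) − (*change to CS*).
- The six remaining cells must satisfy their row and column totals, which leaves one free quantity. Add 1 to each of normal to NCS, NCS to CS and CS to normal, and take 1 from each of normal to CS, CS to NCS and NCS to normal: every planned output stays the same.
- So 8 of 9 independent quantities are recovered.
- If no patient is CS at Visit 2, 6 unknown cells remain and all 6 are recovered; *change to NCS* then means worsening only.

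**4. Do the same for physical examination.** The frequencies are abnormal yes or no.
- Newly abnormal = (abnormal at visit − abnormal at Visit 2) + (*change to normal*). In the arm of step 2 this gives 4 − 2 + 2 = 4 or 4 − 6 + 2 = 0, so that pair can be told apart.
- Total worsening is still not determined. Compare k patients going normal to NCS plus k going NCS to CS with k going normal to CS plus k going CS to NCS. Both give k in *change to NCS*, k in *change to CS*, k abnormal at Visit 2 and 2k abnormal at the visit. The first has 2k worse and 0 better; the second has k worse and k better.
- A three-level table would separate these two cases, because the k baseline abnormalities are NCS in the first and CS in the second. That is why the loss is larger for physical examination than for ECG.

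**5. How often can it arise?** Both ambiguities in direction need a CS finding at Visit 2. For ECG, criterion 6 makes this uncommon but does not rule it out: the exclusion is qualified, and baseline is a later visit than screening. Examination findings are not in that criterion.

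**The case against.** The strongest reply is that little is lost. *Change to CS*, the group that matters most for safety, is always worsening. Newly abnormal counts can be recovered from the planned tables. Clinically significant abnormal findings are adverse events under Protocol 7.3 and are tabulated by preferred term and treatment under SAP 6.5.1. All of this stands and keeps the point small. Two limits apply. The recovery assumes complete pairs, while SAP 6.6.2 imputes no safety data. And it gives newly abnormal patients, not all worsening.

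A reader might infer something stronger: that, because no ECG interval is summarised, the plan is blind to the dog cardiovascular signal and would hide a dose-related slowing of conduction. The documents do not support that.
- Heart rate, which carries the same information as mean RR, is analysed as a continuous net change under SAP 6.5.5.
- Table 6 reports no PR, QRS or QT effect.
- Sinoatrial arrest is a rhythm event, which mean intervals would not count.
- Protocol 1.4.1 calls the heart-rate and diastolic changes mild and seen only at 2500 mg/kg. By the Table 10 conversion that is 2500 x 1666.7/3000 = about 1389 mg/kg, against 2280/60 = 38 mg/kg/day at the higher trial dose for 60 kg: about 37-fold.
- Nothing shows that interval values are recorded.

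A reader might also count the three *no change* cells and call 5 of 9 transitions ambiguous. Those three lose severity, not direction.

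**Conclusion.** The point holds as a minor reporting weakness. One label of four mixes directions (2 of 9 transitions), and one hides whether a persistent finding was clinically significant. For ECG the practical effect is probably small; for physical examination it is larger, though still conditional on CS findings at Visit 2. No efficacy result is affected.

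This rests on three assumptions: that normal, NCS and CS are recorded at every assessment, as the four groups require; that the ECG frequency table uses those three levels and includes Visit 2; and that the mock-up tables, a separate attachment not seen here, do not already show the full cross-table. The absence of interval summaries is a secondary matter and does not carry the point.

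**What to change.** In SAP 6.5.4 and 6.5.6, replace the four groups with a 3x3 shift table by treatment: normal, NCS or CS at Visit 2 against the same at each post-baseline visit and at the worst post-baseline result. State in 6.5.6 that the ECG baseline is Visit 2, since 6.5.7 uses a different one for the C-SSRS. The cost is SAP wording and revised table shells: the data are the same, and a shift table is already planned for the C-SSRS.

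Optionally, given the dog RR and sinoatrial-arrest findings and the commitment to cardiovascular monitoring, list ECG rhythm abnormalities by treatment, and summarise change from Visit 2 in ECG rate and intervals if those values are already recorded. If they are not, the cost of adding them cannot be judged from the documents.

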### **6.5.7 *C-SSRS***

Results of C-SSRS will be presented by part, center, visit, and treatment. The baseline of C-SSRS was set at screening visit (Visit 1).

The analysis for C-SSRS will follow the official guidance “Columbia-Suicide Severity Rating Scale - Scoring and Data Analysis Guide.” The 10 categories will be defined according to 10 binary responses (yes/no) on the C-SSRS, which are:

Category 1 – Wish to be Dead

Category 2 – Non-specific Active Suicidal Thoughts

Category 3 – Active Suicidal Ideation with Any Methods (Not Plan) without Intent to Act

Category 4 – Active Suicidal Ideation with Some Intent to Act, without Specific Plan

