5.2.1 Screening Phase (Visit 1)

The Screening phase will be done within 1-2 weeks period and intended for diagnosing and assessing the patient for possible inclusion in the study and for providing an adequate washout period. The items of physical, rating scales, laboratory examination and drug accountability at screening are outlined below:

- Informed consent
- Subject information, including date of birth, body height and weight
- Medical history, including any clinically significant psychiatric, neurological, gastrointestinal, renal, hepatic, cardiovascular, respiratory, metabolic, endocrine, hematological or other major disorders
- Drug screen, including alcohol, benzodiazepine, amphetamine/MDMA, opiates, cannabinoid, cocaine, phencyclidine, and barbiturate. If a positive result is determined to be caused by prescription of benzodiazepine instead of subject's drug abuse, a 10-day washout period of the prescribed benzodiazepine is required before being treated with investigational products.
- Pregnancy test
- Physical examination: skin, head, neck, eyes, ears, nose, throat, heart, lungs, abdomen (liver, spleen), neurological examination, lymph node and extremities.
- Vital sign: heart rate, blood pressure, body temperature
- ECG
- Hematology: RBC, WBC, platelets, hematocrit, hemoglobin, prothrombin time (PT), partial thromboplastin time (aPTT)
- Blood chemistry: AST, ALT, LDH, total bilirubin, BUN, serum creatinine, free thyroxine (FT4), TSH, sodium, calcium, potassium, HbA1c, LDL, HDL, triglyceride, cholesterol.
- DSM-IV-TR, HAM-D-17, CGI, MADRS, DSSS, HAM-A, C-SSRS and concomitant medication evaluation.

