5.2.3 Part II.- Treatment Period (Visit 2~5) and Follow-up (Visit 6)

Laboratory data and results of other tests and evaluation shall be obtained at screening to determine the appropriateness of subject enrolled in this study. Subjects who meet the eligibility criteria will be enrolled and take study drugs. Baseline data (Visit 2), including physical examination, vital sign, ECG, hematology, blood chemistry, HAM-D-17, CGI, HAM-A, MADRS, DSSS, C-SSRS and concomitant medication evaluation, will be collected before dosing study drug. At visits 2, 3 and 4 (weeks 0, 2 and 4), each subject will be dispensed a supply of study drug sufficient for 2-week treatment period. The subjects will be instructed to take one dose (i.e., two capsules) after a meal thrice daily for every week. Subjects will be assessed every two weeks and receive the study drug for next two weeks till the end of trial. At visits 2, 3, 4 and 5, the safety and efficacy parameters will be evaluated by the following items.

- Physical examination: skin, head, neck, eyes, ears, nose, throat, heart, lungs, abdomen (liver, spleen), neurological examination, lymph node and extremities.
- Vital sign: heart rate, blood pressure, body temperature
- ECG
- Hematology: RBC, WBC, platelets, hematocrit, hemoglobin, prothrombin time (PT), partial thromboplastin time (aPTT). If the interval of visit 1 and visit 2 is within 7 days, Hematology test of visit 2 can be skipped.
- Blood chemistry: AST, ALT, LDH, total bilirubin, BUN, serum creatinine, free thyroxine (FT4), TSH, sodium, calcium, potassium, LDL, HDL, triglyceride, cholesterol. If the interval of visit 1 and visit 2 is within 7 days, Blood chemistry test of visit 2 can be skipped.
- HAM-D-17, CGI, HAM-A, DSSS, MADRS, C-SSRS and concomitant medication evaluation.
- AE/SAE evaluation
- Drug accountability

Follow-up visit will be performed at visit 6 after one week of the last dose administration.

The test items are outlined in the following:

- Physical examination: skin, head, neck, eyes, ears, nose, throat, heart, lungs, abdomen (liver, spleen), neurological examination, lymph node and extremities.
- Vital sign: heart rate, blood pressure, body temperature
- ECG
- Hematology: RBC, WBC, platelets, hematocrit, hemoglobin, prothrombin time (PT), partial thromboplastin time (aPTT)
- Blood chemistry: AST, ALT, LDH, total bilirubin, BUN, serum creatinine, free thyroxine (FT4), TSH, sodium, calcium, potassium, LDL, HDL, triglyceride, cholesterol.

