7 SAFETY ASSESSMENTS

7.1 Specification of Safety Parameters

Safety parameters are outlined as follows:

- Data collected from the physical examinations, vital sign, ECG and laboratory test in scheduled visit
- Adverse events reported
- Serious adverse events reported
- C-SSRS evaluation

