7.2 Methods and Timing for Assessing, Recording, and Analyzing of Safety Parameters

The data obtained before study drug administration in Visit 2 are set as baseline. After the beginning of treatment, the collection of data of safety parameters are performed at planned treatment schedule as section 5.2. AE or SAE will be closely monitored during the study period. CRC shall record these data in CRF in detail. In part I and part II, data are recorded from screening stage to the last visit.

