**Secondary endpoints are:**

- MADRS total score—change from baseline to week 2 and 7
- HAM-D-17, CGI, DSSS and HAM-A—change from baseline to week 2, 4, 6 and 7
- Percentage of partial responders and responders (defined as participants with a 25-50% decrease and a  $\geq 50\%$  decrease from baseline in total score, respectively) in MADRS total score by Week 2, 4, 6 and 7
- Difference in the mean changes of MADRS, HAM-D-17, HAM-A, DSSS, CGI and C-SSRS from baseline to week 2, 4, 6 and 7 between PDC-1421 Capsule and placebo groups.

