**CONFIDENTIAL**

Project No. BLI-1005-002

Statistical Analysis Plan for PDC-1421

“Final” Page 25 of 34

Protocol Version: 2.3

SAP Version: 20180626\_01

Category 5 – Active Suicidal Ideation with Specific Plan and Intent

Category 6 – Preparatory Acts or Behavior

Category 7 – Aborted Attempt

Category 8 – Interrupted Attempt

Category 9 – Actual Attempt (non-fatal)

Category 10 – Completed Suicide

Suicidal ideation is identified if the total score of the five suicidal ideation questions (Categories 1-5)>0. Suicidal behavior is identified if the total score of the five suicidal behavior questions (Categories 6-10)>0. Suicidal ideation or behavior is identified if the total score of the ten suicidal ideation and behavior questions (Categories 1-10)>0.

Changes of suicidal ideation, suicidal behavior, and suicidal ideation or behavior from baseline during treatment will be summarized in a shift-table by visit, center and treatment.

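### The SAP takes the C-SSRS baseline from screening (Visit 1) where the protocol uses pre-dose Visit 2, so pre-dose change enters the on-treatment shift table

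*SAP*

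**What the plan says.** SAP 6.5.7 states: "The baseline of C-SSRS was set at screening visit (Visit 1". It then reduces the scale to three yes/no outcomes (any ideation, any behaviour, either one). Changes in the first two and in "suicidal ideation or behavior from baseline during treatment will be summarized in a shift-table by visit, center and treatment".

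The protocol says otherwise. Section 7.1 lists "C-SSRS evaluation" as a safety parameter, and section 7.2, on the timing and analysis of those parameters, says: "The data obtained before study drug administration in Visit 2 are set as baseline". For Part II, section 5.2.3 is more specific. It lists "Baseline data (Visit 2), including physical examination, vital sign, ECG, hematology, blood chemistry, HAM-D-17, CGI, HAM-A, MADRS, DSSS, C-SSRS and concomitant medication evaluation", all to be collected before the first dose.

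Elsewhere the SAP itself uses Visit 2: for baseline characteristics (6.1), for MADRS (6.4.1) and for the physical examination transition table, which counts "change to clinical significance (CS) for each body system from baseline (Visit 2". SAP 5.4 declares no departure from the protocol's analyses, and the amendment tables in SAP 4 and 11.5 mention no change to the C-SSRS baseline.

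**The concern.** A shift table headed as change during treatment should start from the last status before treatment. Starting from screening adds an untreated interval to the on-treatment change. Protocol 5.2.1 gives the screening phase one to two weeks and intends it partly for washout. It adds that, where a positive screen is put down to a prescription, "a 10-day washout period of the prescribed benzodiazepine is required before being treated with investigational products". Enrolment at Visit 2 rests on Visit 1 measurements (protocol 4.3), and eligibility is scheduled for evaluation only at Visit 1, so the schedule shows no second eligibility check for a change of status in that interval.

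The table matters because it is the only C-SSRS change analysis that SAP section 6 specifies. SAP 5.3.2 does list as a secondary endpoint the "Difference in the mean changes of MADRS, HAM-D-17, HAM-A, DSSS, CGI and C-SSRS from baseline to week 2, 4, 6 and 7" between drug and placebo, but SAP 6.4.2 leaves C-SSRS out and gives it no test. That omission is a separate matter. Here it means that the shift table carries the C-SSRS change assessment alone, and that the mean-change endpoint, if produced, would take the same baseline.

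**Working it through.** **1. Definitions side by side**

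| Source | Variable | Baseline |
|---|---|---|
| Protocol 7.1 with 7.2 | Safety parameters, including C-SSRS; both parts | Visit 2, pre-dose |
| Protocol 5.2.3 | C-SSRS, named; Part II | Visit 2, pre-dose |
| SAP 6.1, 6.4.1, 6.5.4 | Baseline characteristics, MADRS, physical examination | Visit 2 |
| SAP 6.5.7 | C-SSRS | Visit 1 |

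No passage reconciles the last row with the others. The plan gives no figure on this point to reproduce.

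**2. Length of the untreated interval**

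Screening runs one to two weeks, so Visit 1 can precede dosing by about 14 days, or 14 + 2 = 16 with the two-day visit window. It can also be under 7 days, since both documents let the Visit 2 blood tests be skipped when the gap is within 7 days.

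**3. Effect on classification**

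Code status as 0 (absent) or 1 (present) at Visit 1, Visit 2 and an on-treatment visit. There are 2 × 2 × 2 = 8 patterns.

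| V1, V2, on treatment | Shift from V1 (SAP) | Shift from V2 (protocol) | Effect of the SAP rule |
|---|---|---|---|
| 0, 1, 1 | Emergence | No change | False emergence |
| 1, 0, 1 | No change | Emergence | Hidden emergence |
| 1, 0, 0 | Improvement | No change | False improvement |
| 0, 1, 0 | No change | Improvement | Hidden improvement |
| The four with V1 = V2 | Same | Same | None |

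The affected patients are therefore exactly those whose status differs between Visit 1 and Visit 2. Four of eight is a count of logical patterns, not a probability.

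**4. Weight of one affected patient**

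- Part II arm: 60/3 = 20 patients, so 1/20 = 5.0%.
- Part I dose group: 1/6 = 16.7%.
- Part II centre-by-arm cell: SAP 6.6.4 lists six centres and SAP 4 removes one with no enrolment, leaving five. 60/(5 × 3) = 4 patients on average, so 1/4 = 25%. Enrolment by centre is not given, so this is only an average.

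**5. Chance that at least one patient is affected**

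The rate q of status change before dosing is not in the documents. Taking q = 5%, 10% and 20% as an assumed range, with patients independent, P(at least one) = 1 − (1 − q)^n:

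| Group | q = 5% | q = 10% | q = 20% |
|---|---|---|---|
| Part II arm, n = 20: expected number | 1 | 2 | 4 |
| Part II arm: P(at least one) | 64% | 88% | 99% |
| Part I group, n = 6: expected number | 0.3 | 0.6 | 1.2 |
| Part I group: P(at least one) | 27% | 47% | 74% |

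With a Visit 2 baseline, none of these pre-dose changes would enter the shift counts.

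**The case against.** The strongest reply has four parts.

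- **External guide.** Straight after setting the baseline, SAP 6.5.7 says that the analysis follows a published C-SSRS scoring and analysis guide, which might bear on the choice. The guide is not available here, and the SAP does not give it as the reason for Visit 1. If it is the reason, the departure still has to be declared.
- **Span of observation.** The protocol describes safety assessment as running from screening to the last visit. That gives the period of data collection, not the baseline. In protocol Table 12 the same wording covers physical examination, for which the SAP uses Visit 2.
- **Results by visit.** SAP 6.5.7 also presents results by visit, so group counts at Visit 1 and Visit 2 should be visible. They do not cross-classify a patient's Visit 2 status with later visits, so they cannot show whether on-treatment ideation was already present before dosing.
- **Limited consequence.** The table is descriptive, with no test or decision rule. Part I progression turns on serious adverse events, and the primary endpoint is untouched. Patients at high suicidal risk on the MINI are excluded, the benzodiazepine washout is conditional, and nothing in the documents links it to C-SSRS status. The supplied text gives no recall period for the form, and the persistence patterns suit ideation better than behaviour, which consists of events.

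The last group of points stands as a limit on size. None of them removes the contradiction or the misclassification.

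**Conclusion.** The concern holds. The SAP departs from the protocol's C-SSRS baseline without declaring or explaining it, and followed as written it misclassifies every patient whose status differs between Visit 1 and Visit 2. For safety, the most important error is hidden emergence. For Part I the contradiction rests on protocol 7.2; for Part II it rests on 7.2 and 5.2.3.

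Neither the size nor the direction can be derived from the documents. The probabilities above rest wholly on an assumed 5–20% rate of status change and on reading C-SSRS as a comparable yes/no state at each visit. In Part II, where randomisation takes place at Visit 2, pre-dose change should balance across arms in expectation, so it mainly adds noise to the placebo comparison. The within-arm tables, the small by-centre cells and uncontrolled Part I have no such protection. This should be corrected, but it does not threaten the primary analysis.

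**What to change.** In SAP 6.5.7, define the C-SSRS baseline for the shift table as the Visit 2 assessment made before the first dose, in both parts. Count only visits after the first dose as on-treatment; this needs saying because the SAP's Part II flowchart places Visit 2 under the treatment period. Report Visit 1 separately as pre-treatment history, preferably as a Visit 1 to Visit 2 shift. State the same Visit 2 baseline for the C-SSRS mean-change endpoint in SAP 5.3.2.

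If the sponsor has a reason to keep Visit 1, the minimum is to declare and justify the departure in SAP 5.4 and to show the Visit 1 to Visit 2 shift beside the table. That would make the inconsistency open, but the main table would still mix pre-dose and on-treatment change.

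The cost is SAP text and table programming. No new data are needed, since C-SSRS is already scheduled at Visit 2 in both parts.
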